6.3	Compliance	Record the subject's compliance with wearing the study lenses. NOTE: Subjects must have worn lenses for at least 6 hours per day To be counted as a day of wear at this visit the Subject must have worn the study lenses for 6 hours prior to the visit.
6.4	PRO (CLUE and MRD) and CLDEQ-8 Questionnaires	The subject will evaluate the vision characteristics, comfort characteristics, handling characteristics, and visual symptoms of the study lenses using the PRO (CLUE and MRD) questionnaires.
6.5	Ocular Symptoms	Subjects will respond to a verbal open-ended symptoms questionnaire
6.6	Subjective Acceptance	Record whether the subject's distance and near vision with the lenses is acceptable.
6.7	Distance and Near Entrance Visual Acuity	Distance and near Snellen visual acuity will be measured for each eye with the study contact lenses in place. For near measures use the ETDRS 2000 Series Chart 1 or 2. The acuity will be recorded to the nearest letter OD, OS and OU.

Clinical Study Protocol
Johnson & Johnson Vision Care, Inc.

6.8	Visual Performance Distance (4M) Intermediate (64 cm) Near (40 cm)	
Visual performance will be recorded OD, OS, and OU for the following:
 
Distance, Bright Illuminance
 
High and Low Contrast ETDRS Charts 4M- HC#1, HC#2, HC#3 and LC#1, LC#2, LC#3
 
Near, Bright Illuminance
 
Reduced Guillon-Poling Charts Intermediate (64 cm) High Contrast and Low Contrast Near (40 cm) High Contrast and Low Contrast
 
Distance, Dim Illuminance (with Distance goggles)
 
High Contrast ETDRS Charts 4M-HC#4, HC#5, HC#6
 
Near, Dim Illuminance (with Near goggles)
 
Reduced Guillon-Poling charts High Contrast Intermediate (64 cm) and Near (40 cm).
 
NOTE:
 
 • The room illuminance must be between 7.3 and 7.9 EV (394-597 lux). • Distance, HC-1 Chart luminance Acceptable Range 10.5-10.7 EV (181-208 cd/m²). • Guillon-Poling, Near Chart Luminance Acceptable Range 10.8-11.1 EV (223-274 cd/m²). • Do not use the Mesopic filter for Dim luminance (Dim luminance will be simulated by using the goggles) 	
6.9	Binocular Distance Over-refraction and Distance Visual Acuity	
Perform a binocular over-refraction and record the OD and OS results and distance visual acuity.
 
Note: No lens changes are allowed based on the over-refraction.
	
6.10	C-Quant Straylight Meter Testing (Site 1036 only)	Ocular straylight will be measured using the C-Quant OD and OS and record the log (s), Esd and Q values to two decimal places.	
6.11	Corneal Topography and Wavefront	Using the VISIONIX corneal topography and wavefront will be measured over the contact lens OD and OS. The simulated Ks will be	

Clinical Study Protocol
Johnson & Johnson Vision Care, Inc.

	measurement (Site 1036 only)	recorded for the corneal topography and the RMS (day) value for the wavefront.	
6.12	Lens Fit Assessment	
Evaluate and grade lens centration, primary gaze movement, upgaze movement and tightness (push-up test).
 
The subject should not proceed to wear the lenses if any of the following is observed:
 
 • presence of limbal exposure (appearance of clear cornea) in any gaze • presence of edge lift • presence of unacceptable movement (excessive or insufficient) in all three movement categories (primary gaze, upgaze, and push-up). 
NOTE: If lens fit is unacceptable subject will be discontinued from the study. Remove the lenses, and complete the Final Evaluation forms.
	[REDACTED]
6.13	Lens Deposits	Grade and record the amount of front and back surface lens deposits for both eyes.	[REDACTED]
6.14	Lens Wettability	Grade the wettability of the lenses.	[REDACTED]
6.15	Collection of unworn lenses (if applicable)	Collect unworn lenses returned by the subject.	
6.16	Lens Removal	
Have the subject remove the study lenses and store in saline in a labeled glass vial.
 
NOTE: Lenses do not need to be stored in a refrigerator.
	
6.17	Biomicroscopy	
Perform biomicroscopy OD and OS. Slit Lamp Classification Scales will be used to grade the findings.
 
For the conjunctival redness [REDACTED] 0.5 unit increments will be used in the grading.
 
Corneal Staining Assessment [REDACTED] will be graded in 1.0 increments.
 
If the clearance of the fluorescein needs to be expedited, preservative-free rewetting drops may be instilled.
	[REDACTED]

FINAL EVALUATION

Clinical Study Protocol
Johnson & Johnson Vision Care, Inc.

The final evaluation will ordinarily take place immediately following the last scheduled follow-up visit per the study protocol. It may also take place at any point the subject discontinues the study or is terminated from the study.

Final Evaluation		
Step	Procedure	Details
F.1	Distance Subjective Sphero-cylindrical Refraction and Distance Exit Visual Acuity	An optimal, binocular balanced distance sphero-cylindrical refraction will be performed. Record the refraction and distance visual acuity to the nearest letter.
F.2	Subject Disposition	Indicate if the subject completed the study successfully. If subject discontinued from the study indicate the reason.

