1.28	Lens Fit Assessment	Evaluate and grade lens centration, primary gaze movement, upgaze movement and tightness (push-up test). 
 • The subject should not proceed to wear the lenses if any of the following is observed: • presence of limbal exposure (appearance of clear cornea) in any gaze • presence of edge lift • presence of unacceptable movement (excessive or insufficient) in all three movement categories (primary gaze, upgaze, and push-up). NOTE: If lens fit is unacceptable subject will be discontinued from the study. Remove the lenses, and complete the Final Evaluation forms.	
1.29	Modifications	If the subject reports unsatisfactory vision or is unable to obtain 20/30 distance visual acuity OU with the lenses, then a modification must be attempted. If the	

Clinical Study Protocol
Johnson & Johnson Vision Care, Inc.

		
subject reports satisfactory vision with the lenses a modification is not required, however at the Investigator's discretion and based upon their findings on the measured visual acuity and/or over- refraction the investigator may make a modification. Up to two attempts at modification are permitted, if necessary, in order to achieve an acceptable distance and near binocular performance for the subject, and to enable them to wear that particular lens type. Follow the fitting guide allowing for at least 10 minutes of settling time between each lens modification attempted. If modifications are required steps 1.22-1.27 will be repeated for each modification.
	
1.30	Post-Fit PRO (MRD) Questionnaire	
The subjects will evaluate the vision characteristics, comfort characteristics, handling characteristics, and visual symptoms of the study lenses using the PRO (MRD) questionnaire.
	
1.31	Distance and Near Exit Visual Acuity	
Distance and near Snellen visual acuity will be measured for each eye with the study contact lenses in place. For near measures use the ETDRS 2000 Series Chart 1 or 2. The acuity will be recorded to the nearest letter OD, OS and OU.
 
NOTE: The distance visual acuity must be at least 20/30 OU for the lenses to be dispensed.
	

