1.32	Dispensing Criteria	
The following criteria must be met for lenses to be dispensed and if not all are met subject to be discontinued.
 
 • Distance Snellen acuity equal to or better than 20/30 OU • Subject must indicate that the vision is acceptable. • Subject must indicate that the comfort of the lenses is acceptable. • Lenses must have an acceptable general lens fit. 	
1.33	Patient Instructions	Instruct the Subject the following:	

Clinical Study Protocol
Johnson & Johnson Vision Care, Inc.

		
 • The lenses will be worn on a daily wear basis. • Only enough lenses will be dispensed to the subject to wear for the required number of days until their follow-up visit. No additional lenses will be dispensed. • A new lens will be opened and worn each day. • Instruct the subject to bring back all unworn study lenses. • Instruct the subject no cleaning or disinfecting solutions will be used for this lens type. • If determined necessary by the Investigator sterile non-preserved rewetting drops may be dispensed to be used as needed for dryness. • Subjects will be instructed to wear lenses for a minimum of 6 hours a day, every day during the study. • Subjects will be instructed to wear their glasses when not wearing the study lenses. • A patient instruction booklet will be provided. 
NOTE: In the event a lens is lost or damaged, the subject will return to the clinical site for replacement. As much as reasonably possible, a damaged lens and packaging should be returned to the clinical site (wet, if possible) and then returned to the Sponsor. If lens damage is present, complete the Product Quality Complaint Form. The lens will be stored in labeled vial with saline, and clearly differentiated from the other worn lenses that will be shipped back to the Sponsor.
	
1.34	Schedule Follow-up	The subject will be scheduled to return for their follow-up appointment in 3±1 days.	

Clinical Study Protocol
Johnson & Johnson Vision Care, Inc.

		
NOTE: To count the follow-up visit as a day of wear the Subject must have worn the study lenses for 6 hours prior to the visit.
	
--	--	--	--

VISIT 2

The subjects must present to Visit 2 wearing the study lenses. To be counted as a day of wear the lenses need to have been worn for at least six (6) hours prior to the visit.

Visit 2: Treatment 1 Follow-up 1		
Step	Procedure	Details

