4.9	Lens Settling	Allow the study lenses to settle for a minimum of 10 minutes.
4.10	Determine Visual Satisfaction	Determine if the subject's vision is acceptable with the lenses. Allow the subject to look down a hallway or out of a window for distance vision assessments, and for them to read a book, magazine or similar for near vision.
4.11	Distance and Near Entrance Visual Acuity	
Measure the distance and near visual acuity OD, OS and OU. Record the results.
 
For near measures use the ETDRS 2000 Series Chart 1 or 2. The acuity will be

Clinical Study Protocol
Johnson & Johnson Vision Care, Inc.

		recorded to the nearest letter OD, OS and OU.	
4.12	Distance Over-Refraction and Distance Visual Acuity	
Perform a distance over-refraction OD and OS using loose lenses outside of the phoropter under ambient room illumination. The distance over-refraction may also be refined under binocular conditions. Record the results. The results of the distance over-refraction may also be checked for the impact on near vision under monocular and/or binocular conditions.
	
4.13	Lens Fit Assessment	
Evaluate overall lens fit acceptance (acceptable or unacceptable) based on centration, movement and other fitting characteristics.
 
An unacceptable fit is deemed by one of the following criteria:
 
 • limbal exposure at primary gaze or with extreme eye movement; • edge lift; • excessive movement in primary and up gaze; or • insufficient movement in all three of the following conditions: primary gaze, up gaze, and Josephson push up. 
NOTE: If lens fit is unacceptable subject will be discontinued from the study. Remove the lenses, and complete the Final Evaluation forms.
	
4.14	Modifications	
If the subject reports unsatisfactory vision or is unable to obtain 20/30 distance visual acuity OU with the lenses, then a modification must be attempted. If the subject reports satisfactory vision with the lenses a modification is not required, however at the Investigator's discretion and based upon their findings on the measured visual acuity and/or over-refraction the investigator may make a modification.
 
Up to two attempts at modification are permitted, if necessary, in order to achieve an acceptable distance and near binocular performance for the subject, and to enable them to wear that particular lens type. Follow
	

Clinical Study Protocol
Johnson & Johnson Vision Care, Inc.

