		
the fitting guide allowing for at least 10 minutes of settling time between each lens modification attempted.
 
If modifications are required steps 4.7-4.13 will be repeated for each modification.
	
4.15	Post-Fit PRO (MRD) Questionnaire	
The subject will evaluate the vision characteristics, comfort characteristics, handling characteristics, and visual symptoms of the study lenses using the PRO (MRD) questionnaire.
	
4.16	Distance and Near Exit Visual Acuity	
Distance and near Snellen visual acuity will be measured for each eye with the study contact lenses in place.
 
For near measures use the ETDRS 2000 Series Chart 1 or 2. The acuity will be recorded to the nearest letter OD, OS and OU.
 
NOTE: The distance visual acuity must be at least 20/30 OU for the lenses to be dispensed.
	
4.17	Dispensing Criteria	
The following criteria must be met for lenses to be dispensed and if not all are met subject to be discontinued.
 
 • Distance Snellen acuity equal to or better than 20/30 OU • Subject must indicate that the vision is acceptable. • Subject must indicate that the comfort of the lenses is acceptable. • Lenses must have an acceptable general lens fit. 	
4.18	Patient Instructions	
Instruct the Subject the following:
 
 • The lenses will be worn on a daily wear basis. • Only enough lenses will be dispensed to the subject to wear for the required number of days until their follow-up visit. No additional lenses will be dispensed. • A new lens will be opened and worn each day. 	

Clinical Study Protocol
Johnson & Johnson Vision Care, Inc.

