Clinical Study Protocol

Johnson & Johnson Vision Care, Inc.

Example 2:	OD	OS
Spherical Rx:	+4.25 -0.25 x 180	+4.00 D -0.50 x 180
Spherical equivalent (least minus):	+4.25D	+3.75D
Vertex corrected power:	+4.50D	+3.75D
Spectacle Add:		+2.00D
Eye Dominance:		OS
Initial Trial Lens:	+4.50 MED	+3.75 MED

4. Initial Lens Fitting Evaluation

- a) Insert the lenses selected in Section 3 (above). If the exact power is not available, choose the next closest least minus/most plus lens power in your trial set.
- b) Allow the lenses to settle on the eyes for approximately 10 minutes. This allows time for the patient to adapt to the lenses and time for the lens to equilibrate with the patient's tears.
- c) Evaluate the fit of the lenses on the eye. The **Push-up Test** as described below is an important part of the lens evaluation. The following guidelines will be helpful in evaluating the physical fit of the lens:

Characteristics of a Well-fitted Lens

A well-fitted DAILIES TOTAL1® Multifocal (delefilcon A) contact lens satisfies the following criteria:

1. Full corneal coverage and good centration (no limbal exposure). A lens that is decentred > 1 mm, particularly temporal, is less likely to give adequate vision.
2. Lens movement of 0.1 to 0.5 mm should be present to allow tear exchange under the lens during a blink in primary gaze or upward gaze and to avoid variable vision.

Push-up Test:

- This test is a reliable indicator of a good fit. With the patient looking straight ahead, place your index finger on the patient's lower lid and nudge the edge of the lens upward while observing lens movement. Then pull the lid back down and observe the return of the lens.
- A well fitted lens will move freely upward, stopping shortly after passing the limbus and then return freely to its original position.

3. Good comfort.
4. Acceptable visual acuity with over-refraction.

Clinical Study Protocol

Johnson & Johnson Vision Care, Inc.

A tight or steep fit should not be dispensed. If a lens fit is judged to be too steep a flatter lens (larger base curve), if available, should be evaluated. A tight or steep lens fit would display some or all of the following characteristics:

1. Good centration.
2. Insufficient or no lens movement during a blink in primary gaze or upward gaze.

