- Have a third contact lens (near power) to use when critical near viewing is needed.
- Have supplemental spectacles to wear over the monovision contact lenses for specific visual tasks. This is particularly applicable for those patients who cannot meet driver's licensing requirements with a monovision correction.
- Make use of proper illumination when carrying out visual tasks.

Success in fitting monovision can be improved by the following suggestions:

- Reverse the distance and near eyes if a patient is having trouble adapting.
- Refine the lens powers if there is trouble with adaptation. Accurate lens power is critical for presbyopic patients.
- Emphasize the benefits of the clear near vision in straight ahead and upward gaze with monovision.

The decision to fit a patient with a monovision correction is most appropriately left to the eye care professional in conjunction with the patient after carefully considering the patient's needs. All patients should be supplied with a copy of the **Patient Instruction Booklet**, which contains important instructions for the monovision wearer. You can obtain copies of the instruction book by calling customer service in the USA at [name].

Clinical Study Protocol

DISPENSER: Johnson & Johnson Vision Care, Inc.

To help ensure patient success the following steps should be conducted with each patient, even if they have previously worn contact lenses. Even experienced wearers are prone to develop bad habits over time.

DAILIES TOTAL1® brand (delefilcon A) lenses are supplied sterile in foil sealed blister pack containers. Open the foil pack by peeling back the foil lidding material and gently slide the lens out of the container with your finger, or pour the lens onto the palm of your clean hand.

Conduct the following steps with each patient, even if they have previously worn contact lenses:

A. Verification of Lens Fit

Evaluate lens fit and visual response with the lens on the eye. The criteria of a well-fitted lens should be met and the patient's visual acuity should be acceptable. If not, the patient should be refitted with a more appropriate lens.

B. Hygiene and Lens Handling Instructions

Good hygiene and proper lens handling are important factors in achieving safe, comfortable lens wear. Instruct the patient on hygiene and handling of lenses. Patients who are unable to place and remove lenses should not be provided with them.

C. Lens Wear and Replacement Schedules (see Package Insert)

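### Step 1.29 leaves the graded fit assessment out of the steps repeated after a Visit 1 lens change, so a changed eye's only Visit 1 grade is of the replaced lens

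*Combined protocol and SAP*

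**What the plan says.** All steps below are in protocol section 7.2.

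- **Step 1.28** is the graded fit assessment at Visit 1: "Evaluate and grade lens centration, primary gaze movement, upgaze movement and tightness (push-up test". It lists three findings that bar wear: limbal exposure in any gaze, edge lift, and unacceptable movement in all three movement categories. Its note discontinues a subject whose fit is unacceptable.
- **Step 1.29** comes next and allows up to two modifications. It sends the site to the guide, "Follow the fitting guide allowing for at least 10 minutes of settling time between each lens modification attempted", and then sets the repeat: "If modifications are required steps 1.22-1.27 will be repeated for each modification".
- **Step 1.32** lists the dispensing criteria, with discontinuation if any is not met. One of them is "Lenses must have an acceptable general lens fit".
- **Step 4.13** is the Visit 4 fit check: "Evaluate overall lens fit acceptance (acceptable or unacceptable) based on centration, movement and other fitting characteristics". **Step 4.14** says "If modifications are required steps 4.7-4.13 will be repeated for each modification". **Step 5.9** uses the same 4.7-4.13 range, and graded step 5.10 follows it.
- **Step 2.9** (Visit 2 optimization) cites 1.22-1.27, but graded step 2.10 follows it. Step 2.14 then dispenses lenses of the same powers as those just removed.

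Section 2.2 lists mechanical lens fit among the other endpoints, and Table 3 schedules a fit assessment at Visit 1.

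**The concern.** A fit grade taken before the lens is changed describes a lens that the subject does not take home. If nothing later in the visit replaces it, the Visit 1 fit record for that eye is attached to the wrong lens. The explicit stop criteria have also been applied to a lens that is no longer in use. The other fitting and optimization visits avoid this, either by including the fit check in the repeat or by placing the graded fit after the change, so the shorter range in 1.29 looks like a cross-reference that is one step out. The accuracy of a descriptive fit record and the sharpness of one check before dispensing are at stake.

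**Working it through.** The plan gives no figure to reproduce. The inputs are the step order in section 7.2, the limit of two modifications in step 1.29, and the 3±1 day interval in step 1.34.

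**1. Length of the repeated blocks.** Visit 1: 27 − 22 + 1 = 6 steps. Visit 4: 13 − 7 + 1 = 7 steps.

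**2. Matching the steps by content.**

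| Content | Visit 1 | Visit 4 |
|---|---|---|
| Lens selection | 1.22 | 4.7 |
| Insertion | 1.23 | 4.8 |
| Settling | 1.24 | 4.9 |
| Visual satisfaction | 1.25 | 4.10 |
| Distance and near acuity | 1.26 | 4.11 |
| Over-refraction | 1.27 | 4.12 |
| Fit assessment | 1.28 | 4.13 |
| Last step repeated after a change | 1.27 | 4.13 |

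The two sequences run in parallel. The only step in one repeat but not the other is the fit assessment.

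**3. Anything later at Visit 1?** Step 1.30 is a questionnaire, 1.31 exit acuity, 1.32 the dispensing criteria, 1.33 instructions and 1.34 scheduling. None of them grades fit. Step 1.32 asks for a general judgment of fit and does not restate the three findings of step 1.28.

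**4. What is scheduled on the lens finally dispensed**, per eye, for 0, 1 or 2 changes of that eye's lens at the visit. The three kinds of check are kept apart because a grade, a check against named criteria and a general gate are not the same thing.

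| Check on the dispensed lens | Visit 1 | Visit 4 |
|---|---|---|
| Graded fit | 1, 0, 0 (step 1.28) | 0, 0, 0 (4.13 is not graded) |
| Check against named fit criteria | 1, 0, 0 (step 1.28) | 1, 1, 1 (step 4.13) |
| General fit required to dispense | 1, 1, 1 (step 1.32) | 1, 1, 1 (step 4.17) |

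The gap is in the first two rows of the Visit 1 column. The third row has none. Repeating step 1.28 would turn both Visit 1 entries into 1, 1, 1.

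**5. When a grade is next taken.** Step 2.10 falls 3 − 1 = 2 to 3 + 1 = 4 days after Visit 1. It grades the lens in place after step 2.9. If the Visit 1 lens is kept, that is its first scheduled grade. If it is changed again in 2.9, the lens worn home from Visit 1 never has one.

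**6. Where the record is used.** Section 14.7 names only CLUE comfort and handling. No analysis of Visit 1 fit is specified, so a mismatched grade would surface only in the general summaries of section 14.1.

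**The case against.** The strongest reply is that the dispensed lens is already protected. Step 1.32 comes after 1.29 and discontinues a subject whose fit is not acceptable. Step 1.29 also invokes the fitting guide, and the Control guide (Appendix H) has a fit verification at dispensing, "Evaluate lens fit and visual response with the lens on the eye", with criteria that overlap those of 1.28, such as "Full corneal coverage and good centration (no limbal exposure". A reader might infer from the step numbers that changed lenses go home with no fit check. The documents do not support that. What survives is narrower: neither safeguard schedules a new grade or restates all the 1.28 criteria, and Visit 4 has the same dispensing gate yet still repeats its fit step.

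A second reply is that the order is sensible. Changes are driven by vision, and each lens type has one nominal base curve and diameter (Table 1), so a power or ADD change should move fit little. This stands as a reason to call the effect small. It is not stated as a reason for omitting the step, and steps 2.10, 4.14 and 5.9 all check fit after a change.

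Third, Visit 4 records acceptance only, so no graded Test-versus-Control comparison at fitting exists for the edit to restore. That is correct, and none is claimed.

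Fourth, modifications can be made to one eye, as the Control guide's steps for enhancing vision show. The other eye's grade then still belongs to its dispensed lens. This stands, so the point is put per eye and no count is given.

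Fifth, the Test guide (Appendix G) and the fit-grading procedure in Appendix K are redacted and might say more. Nothing is claimed about them; the point rests on the visible step text, which is explicit.

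Last, repeating 1.28 brings in its discontinuation note while a second attempt may still be available. Steps 4.13 and 4.14 already work that way, so this does not defeat the change, but the wording should deal with it.

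**Conclusion.** The point holds as a cheap improvement. For an eye changed at Visit 1, the scheduled grade belongs to the replaced lens, and the specific stop criteria are not scheduled for its replacement. Until step 2.10 the only fit requirement that the protocol steps place on the dispensed lens is the ungraded one in 1.32.

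The size is small: one visit's record for an endpoint with no specified analysis, plus one check before dispensing. The documents do not give the share of subjects or eyes modified at Visit 1, so no number of affected records can be stated.

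Two stronger readings should be resisted. A reader might infer that the primary or secondary results are compromised. They are not: CLUE vision and logMAR are analyzed at the follow-up visits, and the Visit 3 and 6 fit grades are taken on the lens then being worn. A reader might also infer that step 2.9 has the same fault because it cites the same range. It does not, because graded step 2.10 follows it.

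The conclusion assumes that sites follow the written steps and that no redacted text changes the order.

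**What to change.** In step 1.29, change the repeated range from 1.22-1.27 to 1.22-1.28. State that the fit criterion in step 1.32 is judged on the assessment of the final lens, so that the Visit 1 grade on file is that of the lens dispensed. It would help to add whether an unacceptable fit on a first modified lens ends participation or still allows the second attempt. Step 2.9 needs no edit.

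The cost is a short text change and a few minutes of fit grading per modification, at most two per subject at Visit 1. Sample size, analysis and visit schedule do not change.
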